CCMO	Central Committee on Research Involving Human Subjects; in Dutch: Centrale Commissie Mensgebonden Onderzoek
COPP	Observational cohort study ‘Clinical features of COVID-19 in Pediatric Patients’
COREON	Commissie Regelgeving Onderzoek of The Federation of Dutch Medical Scientific Societies
COVID-19	Coronavirus Disease - 2019
CV	Curriculum Vitae
GDPR	General Data Protection Regulation; in Dutch: Algemene Verordening Gegevensbescherming (AVG)
IC	Informed Consent
ICU	Intensive Care Unit
METC	Medical research ethics committee (MREC); in Dutch: medisch-ethische toetsingscommissie (METC)
MIS-C	Multisystem Inflammatory Syndrome in Children
PedsQL	Pediatric Quality of Life Inventory
PROMIS	Patient-Reported Outcomes Measurement Information System
RNAseq	Ribonucleic acid sequencing
(S)AE	(Serious) Adverse Event
SARS-CoV-2	Severe Acute Respiratory Syndrome CoronaVirus-2
Sponsor	The sponsor is the party that commissions the organisation or performance of the research, for example a pharmaceutical company, academic hospital, scientific organisation or investigator. A party that provides funding for a study but does not commission it is not regarded as the sponsor, but referred to as a subsidising party.
UAVG	Dutch Act on Implementation of the General Data Protection Regulation; in Dutch: Uitvoeringswet AVG
WMO	Medical Research Involving Human Subjects Act; in Dutch: Wet Medisch-wetenschappelijk Onderzoek met Mensen

SUMMARY

Rationale: The immune response of children to infection with SARS-CoV-2 is markedly different to the immune response of adults with COVID-19. Children are less likely to develop severe COVID-19, but some children do need supplemental oxygen or intensive care. In rare cases, children who have been infected with SARS-CoV-2 develop a potentially life-threatening post-infectious inflammatory syndrome termed 'multisystem inflammatory syndrome in children' (MIS-C). To better understand and treat these severe sequelae of SARS-CoV-2 infection in children, comprehensive immunological analysis in parallel with the collection of detailed clinical information is needed.

Objective: Primary objective: To obtain a detailed immunological profile of children presenting to Dutch hospitals with acute SARS-CoV-2 infection or with a SARS-CoV-2 related post-infectious inflammatory syndrome. Secondary objectives: (1) To correlate the immunological profiles with detailed clinical parameters. We will collect clinical data in this COPP-IMM study in the same way as in our related observational cohort study 'Clinical features of COVID-19 in Pediatric Patients' (COPP-study). Clinical parameters include: severity of disease, underlying illnesses, age at presentation, clinical syndrome, laboratory parameters at diagnosis, outcome. (2) To identify immunological targets of therapy.

Study design: Multicenter prospective cohort study

Study population: Children age 0-17 years, in- or outpatient in Dutch hospitals with COVID-19 or MIS-C.

Main study parameters/endpoints: We will perform detailed immunological analyses in a two-tiered approach. In the first tier we will do a rapid, more general assessment of the immune system. This will include a detailed phenotypical analysis of the cells of the innate and adaptive immune system using spectral flow cytometry, a multiplex analysis of inflammatory cytokines using Luminex bead arrays and a quantitative and qualitative analysis of anti-SARS-CoV-2 antibodies. Depending on the results of the investigations in the first tier, we will choose which in-depth immunological analyses will be done in the second tier. Investigations in the second tier will focus on the innate immune system, the adaptive immune system (either T-cell responses or B-cell responses) and/or biomarker discovery of serum proteins. The results from the immunological analyses will be correlated to clinical data as collected in the COPP-study.

Nature and extent of the burden and risks associated with participation, benefit and group relatedness:

Blood samples for this study will be collected after confirmation of the diagnosis COVID-19 or MIS-C and after the patient and/or the caregiver have consented for participation. The amount of blood drawn depends on the body weight of the patient, and ranges from 5 to 50 mL. To ensure minimal burden as possible, the collection of the blood sample will be combined with a blood sample collection for routine clinical care and/or will be drawn from an indwelling venous catheter, if possible. If this is not possible, a venepuncture will be done to collect material for this study. In this case, there will be some burden to the patient. To ensure that this burden is minimal, we will apply a topical anaesthetic (lidocaine/prilocaine or lidocaine/tetracaine as per local guidelines) and will instruct local researchers on positive language before and during the procedure.

The risk of this study to the participants is negligible. There is no direct benefit of this study for the participants. The results from this study will benefit the target group, *i.e.* children with COVID-19 or MIS-C, by identifying immunological targets of therapy.

[figure not shown]
1. INTRODUCTION AND RATIONALE

Although in general children are less affected by SARS-CoV-2 infection, a subset of children infected with SARS-CoV-2 develops severe disease (1-5). From the beginning of the pandemic until April 2021, 223 children have been included in our prospective observational cohort study 'Clinical features of COVID-19 in Pediatric Patients' (COPP-study) (www.covidkids.nl/scientific-dashboard).

In adults, severe COVID-19 is characterized by a hyperinflammatory response and cytokine storm. Typically, this hyperinflammatory response does not occur when children are infected with SARS-CoV-2. However, a subset of children is admitted to hospital with COVID-19, and a subset requires supplemental oxygen or even intensive care. In adults with severe COVID-19, treatment with dexamethasone results in better outcomes, but is unknown if children with severe COVID-19 have a similar immunological profile and thus if they would theoretically also benefit from immunosuppression by high-dose corticosteroids.

In rare cases, children develop a post-infectious hyperinflammatory syndrome some weeks after infection with SARS-CoV-2, termed 'multisystem inflammatory syndrome in children' (MIS-C) (6). This potentially life-threatening syndrome can result in myocardial dysfunction and shock, and typically responds well to anti-inflammatory treatment (7). As of April 2021, 60 children have been included in the COPP-study with an inflammatory syndrome suggestive of MIS-C. There are marked differences between the immunological profiles of children with MIS-C and adults with severe COVID-19 (6). However, there has not yet been any study evaluating if the immunological profile MIS-C also differs from the immunological profile of children with severe COVID-19.

In the COPP-study we aim to describe **which** children are at the highest risk of developing severe COVID-19 or MIS-C and **what the exact course of illness** is in these children. In the follow-up study COPP-2, the **late effects** of COVID-19 and MIS-C are evaluated. In the current COPP-IMM study, we will correlate these detailed clinical findings with a **comprehensive and integral analysis of the immune response** of children with COVID-19 or MIS-C.

2. OBJECTIVES

Primary Objective:

To obtain a detailed immunological profile of children presenting to Dutch hospitals with acute SARS-CoV-2 infection or with a SARS-CoV-2 related post-infectious inflammatory syndrome (MIS-C).

Secondary Objectives:

(1) To correlate the immunological profiles with detailed clinical parameters as obtained in our related cohort study 'Clinical features of COVID-19 in Pediatric Patients' (COPP-study).

Clinical parameters include:

- severity of disease
- underlying illnesses
- age at presentation
- clinical syndrome
- laboratory parameters as obtained in routine clinical care
- clinical outcome: days of hospitalization, life-saving interventions, ICU admissions, death, patient reported outcome measures at 6 weeks follow-up.

(2) To determine if there are immunological targets of therapy for children with severe COVID-19 or MIS-C

(3) To determine if hyperinflammation in MIS-C is different from the inflammatory response in severe pediatric COVID-19.

3. STUDY DESIGN

This study is a multicenter, observational, prospective cohort study in hospital-setting in the Netherlands.

Duration of the study: we will collect samples during 18 months. If during this time, we will not have reached the desired number of inclusions (at least 30 children for the immunological part of the study) and SARS-CoV-2 is still prevalent, we will continue our study for another 18 months.

4. STUDY POPULATION

4.1 Population (base)

Currently, 53 hospitals are participating in the COPP-study. From April through December 2020, there have been 157 inclusions (with some children included twice if they were transferred between hospitals). Of the 48 COPP-sites, 13 have currently expressed interest in participating in the COPP-IMM study, including five academic centers. The exact number of children that will be included in COPP-IMM depends on the course of the epidemic, but based on this data, we expect to be able to include about 60 children for the observational part of the study. We expect to be able to obtain informed consent for blood withdrawal in ~50% of these patients, so 30 patients.

4.2 Inclusion criteria

The same inclusion criteria will be used for this COPP-IMM study as for our ongoing COPP-study.

The inclusion criteria of the COPP-study are:

- Age 0-17 years AND
 - Present to an emergency department or outpatient department of a Dutch hospital and/or be admitted to hospital
- AND
- Have at least one positive real-time RT-PCR test on nasopharyngeal, oropharyngeal, sputum or fecal sample for SARS-CoV-2 OR
 - Proof of a (recent) infection with SARS-CoV-2 by positive serology test (IgG/IgM) OR
 - Fulfil a clinical diagnosis(*) of COVID-19, should testing of SARS-CoV-2 yield inconclusive results and/or if testing is no longer possible due to lack of reagents. In these cases there must be an epidemiological link to COVID-19.

(*) This includes:

- signs, symptoms and imaging results indicative of COVID-19 pneumonia without evidence for other causes;
- inflammatory syndrome with a history consistent with recent COVID-19 AND/OR laboratory results consistent with current COVID-19 OR recent COVID-19 (e.g. positive SARS-CoV2-PCR and/or positive serology). This multisystem inflammatory disorder in children and adolescents (MIS-C) is characterized by: fever lasting at least three days, AND at least two of the following: rash or bilateral non-purulent conjunctivitis or mucocutaneous inflammation signs, hypotension or shock, features of myocardial dysfunction, pericarditis, valvulitis, or coronary abnormalities, evidence of coagulopathy, acute gastrointestinal problems, AND elevated markers of inflammation AND no other obvious microbial cause of inflammation (WHO case definition).

In addition to these general inclusion criteria for the clinical part of the study, a minimum body weight of 3 kg is required for blood sampling.

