5. If available, locally **stored samples** will be collected to retrospectively analyze the immunological parameters of the patients in this study, particularly if no consent was obtained for additional sampling for the COPP-IMM study, if an extra blood draw was not feasible for logistic reasons, or if longitudinal analyses are informative.
6. **Follow-up questionnaire** at 12 weeks after start of symptoms (See **Appendix D**). The questionnaires are age-appropriate and contain the following topics: general complaints, remaining symptoms, recovery to normal life, overall health, and quality of life using validated surveys: PedsQL (Pediatric Quality of Life Inventory) and PROMIS (Patient-Reported Outcomes Measurement Information System). PROMIS outcomes are: anxiety, depression, anger, peer relations, sleeping problems, overall health and fatigue. These surveys have been evaluated by the patient support group (Kind & Ziekenhuis). The flow diagram of the follow-up surveys is displayed in **Appendix E**.
7. A separate 2 minutes questionnaire will be sent to children eligible for vaccination against SARS-CoV-2. This questionnaire consists of questions about if a child was vaccinated, and if so, when and if there were any side effects. We will send this questionnaire once a year during the course of this study.

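### Positive IgG/IgM alone admits a child as infected, with no antigen, timing or vaccination condition, so vaccine or old-infection antibody can enter the COVID-19 groups and distort the antibody comparison

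*Protocol*

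**What the plan says.** Protocol section 4.2 requires age 0-17 years, a hospital presentation or admission, and one of three alternatives joined by OR: a positive PCR, "Proof of a (recent) infection with SARS-CoV-2 by positive serology test (IgG/IgM"), or a clinical diagnosis.

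Two safeguards stand in that section, and both belong to the third alternative. The first is "In these cases there must be an epidemiological link to COVID-19". The second, for pneumonia, is "signs, symptoms and imaging results indicative of COVID-19 pneumonia without evidence for other causes". For MIS-C, the SARS-CoV-2 link may be "laboratory results consistent with current COVID-19 OR recent COVID-19 (e.g. positive SARS-CoV2-PCR and/or positive serology"). The definition then adds fever of at least three days, at least two listed features, "AND elevated markers of inflammation AND no other obvious microbial cause of inflammation (WHO case definition").

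Section 3 sets 18 months of sampling. If fewer than 30 children have joined the immunological part and the virus is still prevalent, "we will continue our study for another 18 months".

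On vaccination, section 8.3 item 7 says: "A separate 2 minutes questionnaire will be sent to children eligible for vaccination against SARS-CoV-2". It goes out once a year and asks whether and when the child was vaccinated, and about side effects. The baseline data listed in 8.3 item 2 do not name vaccination.

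Section 10.1 compares cell subsets, cytokines and neutralizing antibodies across mild COVID-19, moderate to severe COVID-19 and MIS-C.

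**The concern.** The primary objective concerns acute SARS-CoV-2 infection and MIS-C. A positive antibody test shows past exposure to antigen. It does not show that the present illness is due to the virus, or that the antigen came from infection rather than a vaccine. The longer the study runs, the more children will carry such antibody for other reasons.

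Three things are at stake:

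- **Group membership.** A child with another illness and incidental antibody has no group of its own in 10.1 and may be counted as mild or moderate to severe COVID-19. This also blurs secondary objective 3, which sets MIS-C against severe COVID-19.
- **The antibody comparison.** Neutralizing antibody is itself compared across the groups. A vaccinated child with a correct diagnosis still carries vaccine antibody into that comparison.
- **The second tier.** Section 8.1.1 lets first-tier contrasts decide how scarce material is used. A choice steered by misplaced children cannot be undone once the material is spent.

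**Working it through.** **1. The protocol's own figures.** Sections 4.1 and 4.4 expect 60 children with about 50% consent to blood sampling: 60 × 0.50 = 30. Section 4.4 splits them as 10 + 10 + 10 = 30. These agree and are not in dispute. Maximum sampling time is 18 + 18 = 36 months.

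**2. Does another section close the serology route?**

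- Section 4.3 excludes children without evidence of current or recent COVID-19. Positive serology is what 4.2 names as that evidence, and *recent* is bracketed and undefined.
- Section 8.3 item 1 admits on a positive test without restricting its type.
- Section 8.3 item 3 takes study blood only once the diagnosis is confirmed, but does not say what confirms it.
- Section 8.3 item 4 counts screened and asymptomatic children as acute phase at presentation, so a compatible illness is not required.
- Section 8.3 item 5 allows stored samples where no study sample was taken.

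None of these separates infection from vaccination or from an old infection.

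**3. Wrong share among serology-only entries.** Let p be the share of otherwise fitting children with true disease, and s the background seropositivity among the rest. Assume every true case tests positive. Then

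wrong share = (1 − p)s / [p + (1 − p)s].

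The documents give neither p nor s; both are assumed. For example, p = 0.5 and s = 0.20 give 0.10 / 0.60 = 16.7%.

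| | s = 5% | s = 20% | s = 40% | s = 80% |
|---|---|---|---|---|
| p = 0.5 | 4.8% | 16.7% | 28.6% | 44.4% |
| p = 0.7 | 2.1% | 7.9% | 14.6% | 25.5% |

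**4. From entries to a group of 10.** If a share q of a group entered on serology alone, the expected number of wrong children is 10 × q × wrong share. The documents do not give q. With p = 0.5:

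| | s = 5% | s = 20% | s = 40% | s = 80% |
|---|---|---|---|---|
| q = 20% | 0.10 | 0.33 | 0.57 | 0.89 |
| q = 50% | 0.24 | 0.83 | 1.43 | 2.22 |

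**5. What a wrong child costs.** As an illustration, compare two means by normal approximation with 10 per group, two-sided alpha 0.05 and a true difference of 1.3 SD. Let f be the share of one group that in fact resembles the other. The difference falls to 1.3(1 − f) and the SD rises to √[1 + f(1 − f)1.3²/2]. Power is 83% at f = 0, 71% at f = 10% (one child) and 59% at f = 20% (two children). The effect size is assumed, and the protocol plans Kruskal-Wallis or ANOVA, so only the direction and rough scale carry over.

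**6. Antibody comparison.** Suppose prior vaccination adds Δ to a child's antibody level on the analysis scale (assumed additive). Each vaccinated child then moves the mean of a group of 10 by Δ/10. The contrast between two groups shifts by Δ × (difference in their vaccinated shares), whether or not the diagnoses are right.

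**The case against.** The strongest reply is that the wording asks for proof of a recent infection, and vaccine antibody is not that. Blood is drawn only after diagnosis, so a child with an unrelated illness should not be sampled. This shows intent and will stop some cases. It does not close the gap, for the reasons in step 2.

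Second, the list in 8.3 item 2 is introduced as a summary, and neither the eCRF nor the appendices are shown, so vaccination may already be captured at entry. The yearly questionnaire asks for dates, and the time of sampling is recorded, so vaccination before sampling can be recovered for responders. This is fair. It still depends on a later reply, and no section links the answer to grouping or analysis. A statistical analysis plan that is not shown may handle serology-only children, but it cannot restore data that were never collected.

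Third, narrowing eligibility would break the deliberate match with COPP: 4.2 uses the same criteria, and 8.1 analyses the clinical data of both studies as one dataset. This stands, and the fix respects it.

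A reader might infer that MIS-C is as exposed as the COVID-19 groups. The text does not support that. Fever, organ features, raised inflammatory markers and the absence of another obvious microbial cause must all hold. What remains is that serology can supply the viral link and that non-microbial mimics are not excluded.

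**Conclusion.** The point holds as a weakness of design. Followed as written, the protocol lets antibody from vaccination or an old infection count as proof of infection, and it names vaccination only in a yearly questionnaire. The risk is clearest for the two COVID-19 groups and for the neutralizing-antibody comparison.

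That the gap exists follows from the text; its size does not. The range of 5% to 44% rests on p = 0.5, seropositivity of 5% to 80% and perfect test sensitivity, and it applies to serology-only entries. At p = 0.7 it is 2% to 26%. A reader might apply the upper shares to a whole group and infer two to four wrong children in ten. That would require nearly the whole group to have entered on serology alone, whereas PCR is the first listed route. The documents give no share by entry route, so no count per group can be stated as a finding.

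The 36 months are likewise a maximum, reached only if recruitment falls short and the virus remains prevalent.

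**What to change.** Keep the inclusion criteria shared with COPP. Make these changes:

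1. Add to the eCRF at inclusion: vaccination status, vaccination dates, and the entry route (PCR, serology with its target antigen, or clinical diagnosis).
2. In the group comparisons of 10.1 and 10.2, do not count a child as acute COVID-19 on serology alone. Show serology-only children separately.
3. Repeat the MIS-C contrast without vaccinated children whose only SARS-CoV-2 evidence is serology that is not anti-nucleocapsid.
4. In the neutralizing-antibody comparison, take vaccination before sampling into account.

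Items 2 to 4 can stand in section 10 or in the statistical analysis plan; item 1 belongs in the protocol and eCRF. The first-tier antibody assay could support the check if its antigens allow.

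Two limits remain. Item 3 assumes that the vaccines in use do not induce anti-nucleocapsid antibody. Such antibody does not date an infection either, so an old infection can still supply the link for MIS-C.

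The cost is two or three eCRF fields and slightly smaller primary groups. No child leaves the cohort, and the pooled dataset with COPP is unaffected.

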4.3 Exclusion criteria

A potential subject who meets any of the following criteria will be excluded from participation in this study:

- No evidence of current or recent COVID-19
- No consent from guardians and/or patient
- For the blood sampling: body weight less than 3 kg.

4.4 Sample size calculation

A formal sample size calculation cannot be done, since it is currently unknown what the variation in immunological response is children with COVID-19 or MIS-C and how this relates to outcome measures. Based on the number of participating sites and the inclusion rate in the first wave of the epidemic, we expect to be able to include at least 60 children in total, and 30 children for the immunological part of the study.

We expect the rate of consent for blood withdrawal to be higher in patients with more severe disease (since the blood can be taken during routine blood withdrawal and no separate venapuncture will be needed). Therefore, based on inclusion rates for the related COPP-study, we estimate we will be able to include at least 10 patients with MIS-C, 10 patients with moderate to severe COVID-19 and 10 patients with mild COVID-19. Clinical information will be available for all of the patients included in the immunological part of the study.

If we will have reached 60 inclusions for the immunological part of the study within the first 18 months of the study, we will do an interim analysis to determine if more inclusions are needed. Since this is an exploratory study, no formal maximal number of inclusions can be given, but based on previous inclusions in de COPP-study and the expected course of the epidemic we do not expect to reach a higher inclusion than 60 in this timeframe.

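### Section 4.4 presents 10 children per group as a minimum, but three such minima use up the whole planned total of 30, and the extension rule looks only at that total

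*Protocol*

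**What the plan says.** Protocol section 4.1 derives the size of the immunological part from feasibility: "we expect to be able to include about 60 children for the observational part of the study", followed by "We expect to be able to obtain informed consent for blood withdrawal in ~50% of these patients, so 30 patients". Section 4.4 says that no formal sample size calculation is possible and repeats the figures: "we expect to be able to include at least 60 children in total, and 30 children for the immunological part of the study".

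Section 4.4 then says that consent to blood sampling should be higher in more severe disease. From this and the COPP-study inclusion rates it estimates "at least 10 patients with MIS-C, 10 patients with moderate to severe COVID-19 and 10 patients with mild COVID-19".

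Two rules act on recruitment:

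- Section 3: samples are collected for 18 months. A further 18 months follow if "we will not have reached the desired number of inclusions (at least 30 children for the immunological part of the study") and the virus is still prevalent.
- Section 4.4: an interim look at whether more children are needed takes place "If we will have reached 60 inclusions for the immunological part of the study within the first 18 months of the study".

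Both rules count the total only. The protocol sets no quota, cap or target for any of the three groups. Section 10.1 compares cell subsets, cytokines and antibodies across exactly these groups, and secondary objective 3 (sections 2 and 10.2) compares MIS-C with severe paediatric COVID-19.

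**The concern.** A minimum in each of three groups needs a total larger than the sum of the minima, because nothing in the plan controls the case mix. Here the sum equals the planned total, so any imbalance puts at least one group below 10.

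There is no power calculation, so 10 per group is the only size the protocol gives for the comparisons it intends to make. A reader will take it as what those comparisons rest on. First-tier differences between groups also steer the choice of second-tier assays (section 8.1.1), so a thin group affects later decisions too. The only rule that could respond, the extension in section 3, does not look at group sizes.

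**Working it through.** **Inputs from the protocol**
- Children expected in the clinical part: 60; consent to blood sampling about 50% (section 4.1).
- Stated minima: 10, 10 and 10 (section 4.4).
- COPP-study to April 2021: 223 children, of whom "60 children have been included in the COPP-study with an inflammatory syndrome suggestive of MIS-C" (section 1). Share: 60/223 = 26.9%.

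**Assumptions (not in the protocol)**
- Children fall into the three groups independently, with fixed shares.
- The shares among sampled children are not given. Two main cases are used: equal thirds, and 26.9% MIS-C with the rest split equally (36.5% each). Two less balanced mixes (MIS-C/moderate to severe/mild) are added to show the range: 27/23/50 and 40/40/20.

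**Step 1. The plan's own figure.** 60 × 0.50 = 30 = 10 + 10 + 10. The total reproduces, with no slack.

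**Step 2. All three groups at 10 or more, given exactly 30 children.** Only 10/10/10 qualifies:

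P = 30!/(10!)³ × (p₁p₂p₃)¹⁰

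- Equal shares: 5,550,996,791,340 / 3³⁰ = 5,550,996,791,340 / 205,891,132,094,649 = 2.7%.
- 26.9/36.5/36.5: 2.0%.
- 27/23/50: 0.5%. 40/40/20: 0.6%.

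The product p₁p₂p₃ is largest when the shares are equal, so 2.7% is a ceiling for any case mix.

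**Step 3. Total not fixed at 30.** If the total is Poisson with mean M (an assumption), the group counts are independent Poisson with means M × pᵢ, and P is the product of the three tails P(X ≥ 10). At M = 30:

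- Equal shares: 0.542³ = 16%.
- 27% MIS-C: 0.292 × 0.656² = 13%.

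At M = 60 the chance is 99% and 96%.

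**Step 4. Total needed (exact trinomial).**

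| Total | Equal shares | 27% MIS-C, rest equal |
|---|---|---|
| 30 | 2.7% | 2.0% |
| 40 | 71% | 59% |
| 45 | 89% | 78% |
| 50 | 96% | 89% |
| 60 | 99.7% | 97.8% |

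The smallest total giving at least 80% is 42 (equal shares) or 46 (27% MIS-C). For 90% it is 46 or 51.

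**Step 5. Smallest group at 30 children.**

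| Mix | Expected smallest group | P(7 or fewer) | P(5 or fewer) | P(4 or fewer) |
|---|---|---|---|---|
| Equal shares | 7.4 | 48% | 11% | 4% |
| 27% MIS-C, rest equal | 7.0 | 57% | 17% | 7% |
| 27/23/50 | 5.9 | 83% | 40% | 21% |

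**Step 6. The extension rule.** A split of 15/10/5 totals 30. It meets the section 3 target ("the desired number of inclusions (at least 30 children for the immunological part of the study"), so no extension follows, and one group has half the stated minimum.

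**The case against.** **Thirty is a floor, not a stopping point.** Sampling runs for 18 months whatever the count, no maximum is set, and an interim look at 60 is foreseen. A reader might infer from the 2.7% that the design almost never delivers 10 per group. The documents do not support that: the 2.7% is conditional on exactly 30 children. With 45 to 60 children and fairly balanced shares the estimate becomes reasonable. What remains is that sections 4.1 and 4.4 plan on 30 and section 3 treats 30 as enough; even with a total varying around 30 the chance is only 13% to 16%.

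**Consent is expected to rise with severity.** A reader might apply 26.9% to 30 and conclude that about 8 MIS-C children should be expected. That assumes equal consent in all groups, against section 4.4. On the protocol's figures 60 × 26.9% = 16 MIS-C children, and 10/16.1 = 62% consent would give 10. An expectation of 10 is therefore compatible with the plan. It is still an average: at a one-third share the chance of 10 or more MIS-C children out of 30 is 57%, and the joint ceiling of 2.7% does not move.

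**The study is exploratory.** No power statement depends on 10 per group, and none is asked for. A reader might see a failed sample size calculation; there is none to fail, and the total of 30 follows correctly from its inputs.

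**Very small groups.** A group of three or four is possible but not typical: four or fewer has a chance of 4% to 7% in the two main cases. The point rests on the ordinary shortfall to about 7.

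**Stored samples** (section 8.3, item 5) may add some children. No number is given, so this cannot be counted on.

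**Conclusion.** The point holds as a mis-stated minimum with a rule that does not protect it. At exactly 30 children the per-group statement holds with probability at most 2.7% for any case mix; with a Poisson total of mean 30 it is about 13% to 16% for the two main cases. Ten per group is at best an average, and the smallest group is expected to be about 7 (about 6 if the mix is less balanced). About 42 to 46 children are needed for an 80% chance that all groups reach 10.

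The ceiling at 30 does not depend on the group shares. The other figures do, and the protocol gives neither the shares among sampled children nor consent by severity. It does not follow that the study will be too small, since the final total may well exceed 30.

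**What to change.** **Section 4.4 (recommended).** Replace the per-group minimum with wording such as: *about 10 per group on average, with the smallest group expected to be about 7 if 30 are sampled*. Do not insert a figure of about 8 MIS-C children, which would conflict with the consent statement in the same paragraph. Cost: one sentence and a less favourable stated figure.

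**Section 3 (optional).** Let the extension decision also consider the size of the smallest group, using the second 18 months already foreseen. This is better framed as a consideration than as a hard trigger. At exactly 30 children a strict requirement of 10 in every group would call for the extension at least 97% of the time (100% − 2.7%), with more blood sampling in children. In simulation, recruiting until every group had 10 took a mean total of about 38 (equal shares) to 41 (27% MIS-C), with 90th percentiles of 46 and 51. These lie within the 60 that section 4.4 contemplates. The downside is that at a total near 30 the extension would usually be used.
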